#### 9.2 SAMPLE SIZE DETERMINATION

The estimated duration of this protocol is 36 months and we anticipate recruiting 1-2 subjects a month over this period.

The primary outcome measure is the MADRS total score. The null hypothesis is that the 95% confidence interval for the effect of drug (TS-161 minus placebo) on MADRS total at 3 weeks, after controlling for baseline scores, will include zero; the alternative hypothesis is that this 95% CI will be less than and exclude zero. We have observed in previous crossover studies of the rapid acting antidepressant ketamine an estimated difference of -6.7 (SE = 1.5) [95%CI: -9.6, -3.76]. This study will be powered to detect an effect within that confidence interval that translates to moderate effect size (difference = -7.5; d = 0.70) on the MADRS total score at end point. While we are primarily interested in identifying drugs with a large effect size, this effect size was selected to balance the risk of an underpowered study if the true effect size were not large and the cost of powering the study to detect a small effect size. Assuming  $\alpha$ =.05, two-tailed, 20 patients with MDD would provide 80% power to detect a drug effect of this magnitude at end point. As discussed, we are interested only in a moderate effect size and have powered the study accordingly. However, if we were to power the study based on the reasonable range of treatment effect observed in the previous studies of rapid acting antidepressants, the sample size requirements would range from 13 subjects for the largest effect in the 95% CI to 67 subjects for the smallest effect. To account for a 25% rate of attrition, either from participants who do not complete the drug-free period or who drop out during the crossover double-blind portion of the study, we will recruit 25 participants. No interim analyses are planned. Secondary analyses with continuous outcomes will likely be sufficiently powered, as we anticipate that the effects on most secondary outcomes will be similar to the primary outcome. However, the power of the study to detect effects on the categorical secondary outcomes (response and remission) will be reduced as categorical outcomes de facto require a larger sample size. SAS 9.4 PROC POWER for paired mean designs was used for sample size calculations.

#### 9.3 POPULATIONS FOR ANALYSES

There will be no interim analysis; the blind will be broken after the accrual goal has been met and all analyses will be based on the full dataset. Analyses will be based on the intent-to-treat (ITT) principle where all randomized subjects who receive baseline and at least one post-baseline assessment during period 1 will be included. The ITT dataset will be used for the primary and secondary analyses.

Safety and tolerability assessments will be based on the safety analysis set which will include all randomized subjects who are given study treatment.

## 9.3.1 Evaluable for Toxicity

All patients will be evaluable for toxicity from the time of their first treatment with TS-161.

#### 9.4 STATISTICAL ANALYSES

## 9.4.1 General Approach

The assumptions of all models will be checked. Specifically, given that the primary model of analysis is the generalized linear model, we will graphically assess the distribution and spread of residuals. We will perform transformation if exploratory data analysis suggests that it will improve adherence to model assumptions; we do not expect that this will be necessary for behavioral outcomes but a log transformation is commonly applied to biological outcomes. For the primary analysis no a priori covariates are specified, except for the baseline values of the outcome as described in this section. Significance will be evaluated at  $p \le .05$ , two-tailed. The primary hypothesis has only one outcome, the treatment effect at week 3, and therefore no correction to alpha (or to p-values) will be made. Following the current guidelines of the American Statistical Association (Wasserstein, Schirm et al. 2019), no threshold will be applied to secondary outcomes of this trial. Instead, parameter estimates will be presented alongside both their 95%

## 9.4.2 Analysis of the Primary Endpoints

The primary aim will be accomplished by assessing the efficacy of three weeks of oral TS-161 (50 to 100 mg/day) compared with placebo in improving overall depressive symptomatology. The primary assessment of efficacy is a comparison of MADRS scores between treatment groups. The MADRS total score is measured at the interval level, and although repeated measurement of the outcome is obtained the primary hypothesis concerns the value at 3 weeks.

The difference between TS-161 and placebo will be examined using a mixed model for repeated measures with restricted maximum likelihood estimation where drug and time are within subjects factors. Fixed effects for drug, time period, and their interaction will be specified. Period-specific baseline scores and the subject-specific average baseline score will be entered as a covariate (Kenward and Roger 2010); no other covariates will be included *a priori*. The degrees of freedom will be corrected using the Kenward-Roger approach. The residual covariance matrix will account for nesting of observations within period for each participant; during the model fitting stage, fit indices (e.g., Schwarz's Bayesian criteria) will be used to determine the most appropriate structure for the residual covariance matrix, including the possibility that it will be specified by drug to allow for heteroscedasticity. Also, during the model fitting stage, a subject-specific (random) intercept will be tested and retained if indicated by model fit indices. During the model

fitting stage, the residuals will be graphically assessed for distribution and spread; if they violate the assumptions of the model then appropriate transformations will be applied before selecting the final model. The analysis will be performed in the ITT sample, and missing data may occur. Maximum likelihood estimation will be implemented, which allows for missingness without excluding the participant; no imputation will be performed. The effect of interest in this model is the effect of drug at the 3-week timepoint (with 95% CI), which will be obtained from the drugby-time interaction using a contrast statement. Cohen's d, calculated using the model-estimated difference between groups, the standard error of that difference, and the degrees of freedom associated with that comparison, will be used to describe the effect size.

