	from baseline on the Hamilton Depression Rating Scale (HDRS), Hamilton Anxiety Rating Scale (HAM-A), Positive and Negative Affect Schedule (PANAS), Snaith–Hamilton Pleasure Scale (SHAPS), and the Temporal Experience of Pleasure Scale (TEPS) scales.  6. To assess the safety and tolerability of a three-week course of TS-161 compared to placebo in a crossover study, by incidence of adverse events (AEs) and total scores using the Clinician Administered Dissociative States Scale (CADSS), Young Mania Rating Scale (YMRS), the Brief Psychiatric Rating Scale (BPRS), vital signs,
	changes in clinical laboratory evaluations, and electrocardiograms (ECGs).
ENDPOINTS:	Primary Endpoint:
	Change from baseline in the MADRS total score
	Secondary Endpoints:
	
 
Proportion of subjects in remission (defined as MADRS total score ≤10).
 

	
 
Proportion of subjects with response (defined as ≥50% reduction from baseline in MADRS total score).
 

	
 
Change from baseline in HDRS, BPRS, CADSS, C-SSRS, HAM-A, PANAS, SHAPS, SSI, TEPS, YMRS total scores.
 

	• Incidence and nature of adverse events; vital signs; weight and body mass index (BMI) changes; physical examination changes; clinical laboratory evaluations; ECG.
	Surrogate Markers of Drug Effect, Target Engagement, and Antidepressant Response
	• Change in magnetoencephalography (MEG) spectral power (gamma power).
	• Change in glutamate levels in magnetic resonance spectroscopy (MRS).
	Change in resting and task based functional connectivity in fMRI.
	Change in peripheral biomarkers.
STUDY POPULATION:	Up to 25 individuals with Treatment-Resistant Depression (TRD) between the ages of 18 and 65 will be enrolled in the study. Participation will not be limited by gender identity or geographic location.
PHASE:	Phase 2 Proof-of-Concept (POC) Clinical Trial
DESCRIPTION OF SITES/FACILITIES	Research will be conducted at the NIH Clinical Center in Bethesda, Maryland, United States.

ENROLLING PARTICIPANTS:	
DESCRIPTION OF STUDY INTERVENTION:	This study will consist of a randomized, double-blind crossover administration of the mGlu2/3 receptor antagonist prodrug TS-161 (50 to 100 mg/day given orally) and placebo.
STUDY DURATION:	The estimated duration of this protocol is 36 months.
PARTICIPANT DURATION:	The total duration of the study, which consists of two phases, is 12 to 16 weeks.

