## 9.4.3 Analysis of the Secondary Endpoints

Secondary objectives are to evaluate the remission and response rates on the primary outcome measure (MADRS). A similar model to the one described above will be employed, with the difference that the outcome distribution will be specified as binary logistic. Because remission/response is determined based on change from baseline within a period, no baseline covariate will be included in the model. The parameter estimate for the effect of drug on remission/response rate at a given time point will be expressed as an odds ratio with a 95% CI. The remaining secondary analyses of clinical outcomes measured on the interval level (HAMD, BPRS, CADSS, C-SSRS, HAM-A, PANAS, SHAPS, SSI, TEPS, and YMRS) will be conducted in the manner described above for MADRS score. Following the current guidelines of the American Statistical Association (Wasserstein, Schirm et al. 2019), no threshold will be applied to secondary outcomes of this trial. Instead, parameter estimates will be presented alongside both their 95% confidence intervals and the raw p-value.

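### The fixed-effects sentence of the primary crossover model does not clearly include Research Condition (1 versus 2); leaving it out costs power and, with unequal sequences, lets part of any between-condition difference into the drug contrast

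*Combined protocol and SAP*

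**What the plan says.** Section 9.4.2 specifies a mixed model for repeated measures "where drug and time are within subjects factors". The fixed effects are given in one sentence: "Fixed effects for drug, time period, and their interaction will be specified". The estimand is the drug effect at 3 weeks, "which will be obtained from the drugby-time interaction using a contrast statement".

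Research condition appears in two other places in that section. One is the baseline adjustment: "Period-specific baseline scores and the subject-specific average baseline score will be entered as a covariate". The other is the covariance: "The residual covariance matrix will account for nesting of observations within period for each participant". Sections 9.4.1 and 9.4.2 both rule out further a priori covariates. The model-fitting stage covers covariance structure, a random intercept and transformation, but not fixed effects.

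Section 9.3 defines the analysis set: "all randomized subjects who receive baseline and at least one post-baseline assessment during period 1 will be included". Section 9.4.3 uses a similar model for response and remission, with this change: "Because remission/response is determined based on change from baseline within a period, no baseline covariate will be included in the model". Remission is an absolute MADRS total of 10 or less (Section 1.1).

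**The concern.** In a two-condition crossover, each patient's drug-minus-placebo difference contains the drug effect plus or minus any difference between Condition 2 and Condition 1. A fixed effect for condition separates the two. On the most natural reading of Section 9.4.2 that effect is absent, because *time period* has to supply the visit factor used in the week-3 contrast.

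The period-specific baseline removes a between-condition difference that acts through baseline. It does not remove one that arises after baseline, such as a different non-drug response the second time round. Nesting within period in the residual covariance models correlation, not a shift in the mean.

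Unequal sequences are foreseeable. Patients who still meet response after the extended washout are withdrawn before Condition 2 (Sections 4.2 and 8.3). Treated withdrawals are not replaced (Section 7.2). Section 6.5 states no allocation ratio or blocking. At stake is the single confirmatory test, with about 20 completers. Remission is more exposed than response: response has the period baseline in its definition, whereas on the visit reading nothing in the mean model for remission adjusts for condition.

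**Working it through.** **Inputs.** From Section 9.2: difference -7.5, d = 0.70, 20 patients, two-sided alpha 0.05, paired-means method. The implied SD of the paired difference is 7.5/0.70 = 10.71. The between-condition difference beyond baseline, π (Condition 2 minus Condition 1 at week 3), is not in the documents; 2, 4 and 6 points are assumed.

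**The plan's own figure.** An exact paired t calculation with d = 0.70 needs 19 patients for 80% power, close to the stated 20. Power at n = 20 is 84.4%.

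**Model.** With δ the drug effect, the expected paired difference is δ + π for drug-second patients and δ − π for drug-first patients.

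- *Without the term:* the estimate is the mean of all differences (19 df). Its expectation is δ + π × (n drug-second − n drug-first)/n.
- *With the term:* the estimate is the average of the two sequence means (18 df). It is unbiased, with SE = (10.71/2) × √(1/n₁ + 1/n₂).

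**Equal sequences (10:10).** There is no bias, but the expected variance without the term rises to 10.71² + π² × 20/19. At 4 points this is 114.8 + 16.8 = 131.6 (SD 11.5); at 6 points, 114.8 + 37.9 = 152.7 (SD 12.4). Simulated power without the term is 83.3%, 80.7% and 75.8% at 2, 4 and 6 points. With the term it is 84.1%.

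**Unequal sequences, completers only.** The share of π entering the contrast is 4/20 = 20% at 12:8, 6/20 = 30% at 13:7 and 8/20 = 40% at 14:6. For π of 4 to 6 points:

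| Split | Estimate if weakened (power) | Estimate if strengthened (power) | Power with term |
|---|---|---|---|
| 12:8 | -6.7 to -6.3 (71 to 60%) | -8.3 to -8.7 (88%) | 82.6% |
| 13:7 | -6.3 to -5.7 (66 to 51%) | -8.7 to -9.3 (91 to 92%) | 80.6% |
| 14:6 | -5.9 to -5.1 (60 to 42%) | -9.1 to -9.9 (94 to 95%) | 77.4% |

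With no drug effect, two-sided rejection at 13:7 is about 5.3% for 2 points and 6.0 to 6.8% for 4 to 6 points. At 12:8 it stays below 5%. All these figures are conditional on the split.

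**Averaged over simple randomisation (assumed).** With sequence a coin flip per patient, the mean estimate is -7.50 and null rejection 5.0% at every shift. Power without the term is roughly 83%, just under 80% and 74% at 2, 4 and 6 points.

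**Keeping patients with Condition 1 data only.** Take 12 randomised per sequence, with 4 lost from one sequence after Condition 1 (12:8 among completers). Generalised least squares puts 10% of π into the contrast at within-subject correlation 0 and 17% at 0.7. A mid-range value is about 14%, against 20% for completers only.

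**Baseline-carried difference.** At 12:8 with the baseline difference as covariate (assumed SD 5, slope 0.7) and the term omitted, a 5-point drop acting only through baseline gives -7.50, so no bias. A 4-point shift beyond baseline gives -6.70.

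**Is a main effect enough?** If π grows linearly over the visits (assumed), a single constant condition effect still leaves 12 to 13% of the week-3 shift in the contrast at 12:8 and 23 to 27% at 14:6. The leakage reaches zero only with condition-by-visit terms. The with-term figures above come from a week-3 analysis, so they correspond to a model with those terms, or to a constant shift.

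**Remission.** Assume 20% remission in Condition 1, a between-condition odds ratio of 2 (33.3% in Condition 2) and no drug effect. At 12:8 the two arms expect (12 × 20 + 8 × 33.3)/20 = 25.3% and (8 × 20 + 12 × 33.3)/20 = 28.0%. The apparent drug odds ratio is 0.87, or 1.15 in the other direction.

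**The case against.** The strongest reply is that a comma was lost and the authors meant drug, time and period. Elsewhere in Section 9, period alone means research condition, so this is plausible, and a reader should not infer that the plan definitely omits the term. Even so, *their interaction* does not then say which of the three factors interact, and two analysts could fit different models. The sentence needs rewriting on either reading.

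A second reply is that baseline adjustment already deals with period. It does for a difference carried by baseline, which is why the point is limited to a difference beyond baseline.

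A third is that the bias and type I error figures describe particular splits. This stands. A reader might infer that the planned test is biased or runs above 5%. The documents do not support that: they give no between-condition difference and no sequence split, and under simple randomisation the test without the term is valid on average. Silence on blocking does not establish simple randomisation either. Nor does responder withdrawal support an inflated type I error, because with no drug effect it is not expected to differ by sequence. If the drug works, it would tend to remove drug-first patients, so imbalance need not be chance alone.

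Finally, remission is a secondary outcome with no significance threshold, and its odds ratios rest on three assumptions. They show direction rather than likely size.

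**Conclusion.** The point holds as a defect of specification that should be fixed. On its most natural reading the confirmatory crossover model has no fixed effect for research condition, and on the alternative reading its interactions are undefined.

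If the term is left out, the dependable consequence is lost power: about 1, 3 and 8 percentage points at assumed differences of 2, 4 and 6 points with equal sequences. A distorted drug estimate needs both a difference beyond baseline and an unequal split. Its direction depends on which sequence has more completers and whether Condition 2 scores run lower or higher. Keeping patients with Condition 1 data only reduces it. With no difference beyond baseline, omission does no harm. The calculations are week-3 paired approximations, apart from the least-squares checks, and do not run the full repeated-measures model.

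**What to change.** In Section 9.4.2, replace the sentence with: *Fixed effects: drug, visit, drug-by-visit, research condition (period 1 vs 2), and research condition-by-visit.* Keep the planned baseline covariates. Carry research condition into the Section 9.4.3 models, above all the one for remission. Make the change before the blind is broken.

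This needs no new data and no change of design. With seven post-baseline MADRS visits (Section 1.4), the added terms use 1 + 6 = 7 fixed-effect parameters. If there is in fact no between-condition difference, power for the week-3 contrast falls from 84.4% by about 0.2 points at 10:10, 1.7 at 12:8, 3.7 at 13:7 and 6.9 at 14:6 (paired approximation).

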#### 2.2 BACKGROUND

# 2.2.1 Ketamine Induces Rapid Antidepressant Effects, but Produces Dissociative Side Effects and has the Potential for Abuse

Mood disorders (MDD and bipolar disorder [BD]) are common, chronic, recurring, serious mental illnesses associated with significant morbidity, and often become life-threatening. A variety of antidepressants have been developed; unfortunately, these medications take weeks to months to achieve their full effects and in the meantime, patients continue to suffer from their symptoms and continue to be at risk of self-harm as well as harm to their personal and professional lives. Although a significant proportion of patients usually respond to currently available medications within three

to four weeks, remission rates are usually low at this point and may take several more weeks to become manifest (Entsuah, Huang et al. 2001). Moreover, up to one-third of patients still do not respond with four consecutive trials of antidepressants. A more rapidly acting antidepressant medication in TRD would significantly impact the treatment of depression and have major health care implications.

In subjects with TRD, ketamine is the only pharmacological treatment that has antidepressant effects that both occur within hours and are sustained for one week or more with a single-administration (Zarate, Singh et al. 2006, Kishimoto, Chawla et al. 2016). In the 2006 study, of 17 subjects, 71% of participants met criteria for antidepressant response (a 50% decrease in HDRS scores), and 29% achieved remission (≤7 HDRS) at 24 hours following infusion of ketamine. Six (35%) subjects maintained response to ketamine for at least one week; in contrast, no subject on placebo responded at Day 1 or Day 7. In a recent study, we found that the antidepressant efficacy of ketamine lasted at least 11 days with single administration in subjects with TRD (Nugent, Ballard et al. 2019). Within six hours to one day, a single ketamine infusion led to response rates comparable to those seen following eight weeks of treatment with monoaminergic based antidepressants. Furthermore, ketamine induced remission in approximately one-third of subjects within one day, which is in stark contrast to that of monoaminergic-based approaches, which usually require 10-14 weeks of chronic daily usage to produce similar remission rates (Trivedi, Rush et al. 2006).

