#### 4.2 SCIENTIFIC RATIONALE FOR STUDY DESIGN

This study will use a double-dummy blind dosing design, all subjects will receive two capsules in the AM approximately 30 minutes after start of breakfast, and dose adjustment, if required due to intolerance, will be done blindly. A flexible dose design (50 or 100 mg/day) will be used in this study since this type of dosing permits better assessment of safety and efficacy than does a fixed dose, especially when this compound has not been previously tested in subjects with major depression. The maximum daily dose of TS-161 administered in this study will be 100 mg/day. All subjects except those who are responders at the end of the first treatment condition

will cross over. To avoid carry-over effects between the different test sessions, there will be an interval of 14-21 days, pending response to Research Condition 1. Subjects will then be blindly crossed over to the second treatment condition (either TS-161 or placebo) for another three weeks. Subjects maintaining response to Research Condition 1 after two weeks will receive an additional one-week washout before being crossed over to Research Condition 2. Subjects maintaining response (50% improved from baseline on the MADRS) after this additional week will be withdrawn from the study and will receive standard clinical treatment.

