## 5 STUDY POPULATION

## 5.1 INCLUSION CRITERIA

In order to be eligible to participate in this study, an individual must meet all of the following criteria:

- 1. Ability of subject to understand and the willingness to sign a written informed consent document. To verify this, subjects must score ≥ 80% on the consent quiz (Appendix A).
- 2. Stated willingness to comply with all study procedures and availability for the duration of the study.
- 3. Aged 18 to 65.
- 4. Subjects must fulfill DSM-IV or DSM-5 criteria for MDD, single episode or recurrent without psychotic features, based on clinical assessment and confirmed by a structured diagnostic interview (SCID-P). Subjects must be experiencing a current major depressive episode of at least 4 weeks duration.
- 5. Subjects must have an initial score of  $\geq$  20 on the MADRS and a YMRS score of  $\leq$  12 within one week of the start of Phase I and upon entry into Phase II.
- 6. Ability to take oral medication and be willing to adhere to the TS-161 regimen.
- 7. Subjects must have a current or past history of lack of response to at least one adequate antidepressant trial (may be from the same chemical class) in the current major depressive episode, operationally defined using the modified-Antidepressant Treatment History Form (ATHF)); a failed adequate trial of ECT [or TMS] would count as an adequate antidepressant trial.
- 8. For females of reproductive potential: use of contraception starting at the time of enrollment and agreement to use such a method during study participation and for an additional 4 weeks after the end of Phase II (see Contraception Guidance, Appendix D).
- 9. For males of reproductive potential: use of condoms or other methods from the time of enrollment to ensure effective contraception with partner, and for an additional 90 days after the end of Phase II (see Contraception Guidance, Appendix D).
- 10. Agreement to adhere to Lifestyle Considerations throughout study duration

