#### 8.3 TS-161 AND PLACEBO ADMINISTRATION

All participants will use this dose range unless tolerability issues ensue. A randomization code will be generated by the unblinded statistician. The study site pharmacist(s) responsible for study drug dispensation will also be unblinded.

This study will use a double-dummy blind dosing design, all subjects will receive two capsules in the AM after start of breakfast, and dose adjustment, if required due to intolerance, will be done blindly. Instructions for the preparation of study drugs are provided in a separate manual. A flexible dose design (50 or 100 mg/day) will be used in this study since this type of dosing permits better assessment of safety and efficacy than does a fixed dose, especially when this compound has not been previously tested in subjects with major depression. All subjects except those who are responders at the end of the first Research Condition will cross over. To avoid carry-over effects between the different test sessions, there will be an interval of 14-21 days, pending response to Research Condition 1. Subjects will then be blindly crossed over to the second Research Condition (either TS-161 or placebo) for another three weeks.

No subject will receive more than 3 weeks of TS-161. All subjects who discontinue the study or who complete Study Phase II will then receive either short-term standard clinical treatment (for up to 2 months) or the opportunity to participate in another research protocol. Subjects maintaining response to Research Condition 1 after two weeks will receive an additional one-week washout before being crossed over to Research Condition 2. Subjects maintaining response (50% improved from baseline on the MADRS) after this additional week will be withdrawn from the study and will receive standard clinical treatment.

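### Does the undefined subject-average baseline for participants without a second-period baseline require a change to the primary model?

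*Combined protocol and SAP*

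**What the plan says.** The primary analysis (Section 9.4.2) is a mixed model for repeated measures with drug, time period and their interaction. On covariates it states: "Period-specific baseline scores and the subject-specific average baseline score will be entered as a covariate". It cites a methods paper on baseline covariates in crossover studies for this choice. On missing data it relies on maximum likelihood, "which allows for missingness without excluding the participant; no imputation will be performed".

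Section 9.3 defines the analysis set: "all randomized subjects who receive baseline and at least one post-baseline assessment during period 1 will be included". A participant who never starts Research Condition 2 is therefore in the primary analysis.

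Sections 4.2 and 8.3 describe who may not reach Condition 2. One sentence reads: "All subjects except those who are responders at the end of the first Research Condition will cross over". Later sentences are narrower: "Subjects maintaining response to Research Condition 1 after two weeks will receive an additional one-week washout before being crossed over to Research Condition 2", and those still responding "after this additional week will be withdrawn from the study and will receive standard clinical treatment". Section 9.2 also allows for 25% attrition, and Section 7.2 does not replace treated participants who leave.

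No part of Sections 9.3 or 9.4 says how the subject average is computed when only one period's baseline exists.

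**The concern.** A mixed model conditions on its covariates. The likelihood accommodates a missing outcome, but a row with a missing covariate is removed. If the average is taken to need both baselines, a participant with Condition 1 data only loses every row, contrary to the ITT definition and to the assurance in Section 9.4.2. With 20 to 25 randomised, losing several people matters. If those lost are Condition 1 responders, exclusion depends on outcome and could pull the drug effect toward zero. The continuous secondary scales use the same model and inherit the gap.

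A second worry needs no missing data. The average includes a score taken after Condition 1 treatment, so Condition 1 outcomes are adjusted for something that treatment may have changed. The MADRS entry threshold applies "within one week of the start of Phase I and upon entry into Phase II", and no recheck before Condition 2 is stated, so some persisting improvement could enter the second baseline.

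**Working it through.** **The plan's own figure.** Section 9.2 gives a difference of -7.5 and d = 0.70, so the SD of the paired difference is 7.5/0.70 = 10.71. Exact paired-t power at two-sided 0.05 is 82.3% for n = 19 and 84.4% for n = 20, so the stated 20 is adequate. The implied error SD per period is 10.71/√2 = 7.58.

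**Records at stake.** Take 25 ITT participants of whom 5 lack a Condition 2 baseline (illustrative). If both baselines are required, the model uses 20 participants and 20 × 2 = 40 period records. With the available average it uses 25 participants and 40 + 5 = 45 records.

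**Which reading fits the text?**
- Requiring both baselines excludes people whom Section 9.3 includes and breaks the no-exclusion statement.
- Filling in a second baseline breaks the no-imputation statement.
- Averaging the baselines that exist breaks neither, and it is computable for every ITT participant. For one-period participants the two covariates coincide, which causes no fitting problem because they differ for everyone else.

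**Size.** Week-3 crossover simulation, compound-symmetry REML, true effect -7.5. These inputs are not in the documents: baseline mean 32 and SD 5 (truncated at 20), subject SD 6, washout-score noise SD 4, placebo change -4 or -8, and 15% other drop-out. Persistence is the share of the Condition 1 change still present at the end of washout. Monte Carlo error is about 0.02.

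| Who leaves; placebo change; persistence | Complete data | Dropped | Available average | Condition 1 baseline only |
|---|---|---|---|---|
| Sustained responders; -4; 0% | -7.50 | -7.50 | -7.50 | -7.49 |
| Sustained responders; -4; 20% | -7.07 | -7.06 | -7.10 | -7.50 |
| Sustained responders; -4; 50% | -6.11 | -6.12 | -6.58 | -7.48 |
| Sustained responders; -8; 80% | -5.70 | -5.70 | -7.62 | -7.51 |
| All responders; -4; 0% | -7.51 | -6.61 | -7.51 | -7.53 |
| All responders; -8; 0% | -7.48 | -6.36 | -7.46 | -7.49 |

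With all seven post-dose ratings in the model, the available average without persistence gives -7.48 to -7.60. Dropping gives -6.75 to -6.85 if all responders stay out. Under the sustained rule it moves the complete-data estimate by at most 0.23.

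A second simulation used different assumptions (25 randomised, subject SD 5, baseline noise SD 3, no persistence, Monte Carlo error about 0.06). Random 20% loss gave -7.47 (SE 2.34) dropped against -7.46 (SE 2.21) kept. With 10% random loss plus 25%, 50% or 100% of Condition 1 responders withdrawn whatever their washout score, dropping gave -7.27, -7.01 and -6.15. Keeping them gave -7.48, -7.49 and -7.48.

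**Precision.** Under the sustained rule at 25 randomised with no persistence, the SD of the week-3 estimate is 2.47 dropped and 2.41 kept.

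**The post-treatment covariate.** Without persistence the planned covariates recover -7.5. At 20% the shift is 7.50 - 7.07 = 0.43 (week 3), or about 0.2 with all visits. The large shifts in the table need 50 to 80% of the change to survive a 14 to 21 day washout without touching Condition 2 outcomes. If persisting improvement also reaches those outcomes, using only the Condition 1 baseline loses its advantage:
- 20% persistence, half carried (week 3): -7.10, against -7.06 for the available average.
- 20% persistence, fully carried (week 3): -6.79 against -7.09.
- 50% persistence, 60% carried (all visits): -6.54, against -6.78 for the planned covariates with complete data.

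**The case for a change.** The strongest case for a change is that an unstated rule leaves room to choose after unblinding, and that the choices can disagree. A two-baseline average, an available average, and one that counts the end-of-washout MADRS of withdrawn responders are all conceivable. Section 1.4 lists a Day 34 rating under Condition 2, so that last score may well exist. The single Condition 1 baseline is held by every ITT participant, costs nothing to collect and, absent carry-over, stays near -7.5 in every setting tried.

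Part of this stands. The rule is not written down, and the likelihood assurance does not by itself cover a missing covariate. But the text already excludes the damaging reading. Counting the washout score simply restores something close to the complete-data fit (-6.24 against -6.11 at 50% persistence, placebo change -4), and makes no difference without persistence.

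The substitute covariate is a larger step than a wording change. It would remove the period-specific baseline too and adjust Condition 2 outcomes for a score at least five weeks old, although the hypothesis in Section 9.1.1 controls for baseline. Its advantage depends on persistence without carry-over. The documents give no figure for either. Section 2.2.1 reports that "we found that the antidepressant efficacy of ketamine lasted at least 11 days with single administration in subjects with TRD", and Section 2.2.2 cites about one week for this drug class in animals. Both are shorter than the washout, though both follow single doses and are an imperfect guide to three weeks of daily dosing.

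**Conclusion.** This is a missing definition that an analyst would fill sensibly, by averaging the baselines available so that Condition 1 rows stay in. It is the reading consistent with Sections 9.3 and 9.4.2 together. Without persistence it recovers the true effect (-7.46 to -7.60 against -7.5) under either account of who is withdrawn. Even the contrary reading changes little if only sustained responders leave: at most 0.02 at week 3 and 0.23 with all visits, against an SD of about 2.4. A bias near one point requires dropping participants against the plan's own words and also keeping every responder out. Withdrawing a quarter or half of responders regardless of washout score, and dropping them, would cost about 0.2 to 0.5.

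The post-treatment adjustment is a fair trade-off within a cited method. The alternative can be better or worse depending on quantities the documents do not supply.

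All sizes rest on the assumed variances, drop-out and persistence listed above. Separately, the sentences in Sections 4.2 and 8.3 on which responders cross over contradict each other and must be reconciled. The conclusion about the covariate does not depend on how that is settled.
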